1. OBJECTIVES

1.1 Study Design

This is a pilot trial to assess the feasibility of using proton radiation to treat breast cancer following surgery (mastectomy or breast-conserving). The intent of this study is to exploit the properties of protons for delivery of radiation therapy to the chest wall and regional lymphatics, including internal mammary nodes, without need for removal or manipulation of breast reconstruction and/or to decrease cardiac exposure to radiation and to form the basis for future studies. This study is intended to determine the feasibility of both double scattered 3D conformal protons as well as intensity modulated proton therapy (IMPT).

1.2 Primary Objectives

1.2.1 To determine the feasibility of using proton radiation for the treatment of invasive breast cancer following surgery (mastectomy or breast-conserving) based on the occurrence of grade 3 or higher radiation pneumonitis or any grade 4 toxicity within 3 months after the completion of radiation treatment. The goal is to enable women with breast reconstruction to undergo radiation therapy without removal or manipulation of reconstruction in order to allow radiation delivery without excessive pulmonary and cardiac dose and to enable patients with unfavorable cardiac anatomy (as defined by $\geq 5\%$ of the heart receives ≥ 20 Gy and/or LAD receives ≥ 20 Gy with conventional planning) to undergo chest wall irradiation with better cardiac sparing.

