This document is confidential. Do not disclose or use except as authorized.

treated with oral corticosteroids. There were neither hospitalizations nor deaths from pneumonitis, which means that the incidence of 4.1% may be regarded as the incidence of RTOG grade 3 events. The Duke report predated the widespread use of taxane chemotherapy, but AC chemotherapy or cyclophosphamide, methotrexate, and 5-fluorouracil was given to 42% of the group, which resulted in a RP rate of 3.8%. Beal and McCormick reported a small series of 38 node-positive breast cancer patients treated with surgery, adjuvant (AC, T), followed by comprehensive radiation therapy at MSKCC.³⁸ No cases of RP were seen in this group after a median follow-up of 28 months. However, none of the patients in this study required irradiation of the internal mammary lymph nodes.

CONFIDENTIAL

This document is confidential. Do not disclose or use except as authorized.

Summary of Retrospective Studies Reporting RP After Breast RT:					
Author	Institution	Publication Year	n	Overall RP Reported (RTOG Grade)	Subset with RTOG Grade 3
Taghian	MGH	2001	41	14.6% grade 2-3	12%
Lind	Duke	2002	294	4.1% grade 3	4.1%
Voduc	British Columbia	2004	77	2% grade 2-3	2%
Yu	MDAH	2004	189	5% grade 2-3	1%
Beal	MSKCC	2005	38	0%	0%

In order to assess the feasibility endpoint in the proposed study, we are most interested in capturing incidences of RP that requires corticosteroids or hospitalization (RTOG grade 3-5). However, no series reported any fatalities or grade 4 events from RP after breast RT, so serious pneumonitis in this population appears to be limited to RTOG grade 3 events. The weighted average for grade 3 RP in these series using the RTOG scale is around 3.3%. Again, not all of the reported series included patients who required internal mammary lymph node radiation.

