5.3 General Concomitant Medication and Supportive Care Guidelines

Concomitant chemotherapy as dictated by protocol or the treating physician is allowed. All appropriate non-investigational supportive care medications or treatments may be used for optimal symptom management.

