6. EXPECTED TOXICITIES AND DOSING DELAYS/DOSE MODIFICATIONS

The CTEP Active Version of the NCI Common Terminology Criteria for Adverse Events (CTCAE) will be utilized for AE reporting. The CTEP Active Version of the CTCAE is identified and located on the CTEP website at

http://ctep.cancer.gov/protocolDevelopment/electronic_applications/ctc.htm
<https://phsexchweb.partners.org/exchweb/bin/redir.asp?URL=http://ctep.cancer.gov/protocolDevelopment/electronic_applications/ctc.htm>. All appropriate treatment areas should have access to a copy of the CTEP Active Version of CTCAE. If possible, symptoms should be managed symptomatically. In the case of toxicity, appropriate medical treatment should be used.

All radiation related grade 2 and greater adverse events experienced by participants will be collected from the time of the start of radiation and throughout the study and until the final study visit. Participants continuing to experience toxicity at the off study visit may be contacted for additional assessments until the toxicity has resolved or is deemed irreversible.

It is anticipated that toxicities will be decreased with proton radiation.

CONFIDENTIAL

This document is confidential. Do not disclose or use except as authorized.

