12.1 Study Design/Endpoints

This is a pilot study substituting proton radiation for photon radiation, seeking to show the feasibility of proton radiation and to assess the rate of acute, sub-acute and late toxicities during and after proton radiation to the left chest wall and regional lymphatics. It is anticipated that patients undergoing proton radiation will not have increased toxicity compared to patients who have historically undergone photon radiation.

Proton radiation will be considered to be feasible as adjuvant treatment for invasive breast carcinoma in each cohort following surgery if the rate of grade 3 or higher radiation pneumonitis within 3 months of treatment were no more than 5%, within the range associated with conventional techniques of adjuvant radiation. In addition to radiation pneumonitis, the feasibility of proton radiation will also be compromised by any grade 4 effect occurring within 3 months of treatment, as well as skin toxicity and pericarditis. If 2 or more of the initial 12

CONFIDENTIAL

This document is confidential. Do not disclose or use except as authorized.

patients were to experience grade 3 or higher radiation pneumonitis or any grade 4 toxicity within 3 months of finishing radiation, accrual to a cohort will not continue further. The probability of stopping early is only 12% if the underlying rate of grade 3 or higher radiation pneumonitis or any grade 4 toxicity were truly 5%. Otherwise, the cohort will proceed to enroll a total of 26 patients and declare the feasibility of proton radiation if no more than 2 of them were to experience grade 3 or higher radiation pneumonitis or any grade 4 toxicity within 3 months after treatment. The two-stage design provides 81% power to accept that proton radiation is associated with a 5% rate of grade 3 or higher radiation pneumonitis or any grade 4 toxicity in a treated cohort. However, the probability is only 20% for declaring the feasibility of proton radiation if the underlying rate grade 3 or higher radiation pneumonitis or any grade 4 toxicity were truly 15%.

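### Read literally, the primary event does not count a fatal toxicity other than pneumonitis; its time window, attribution rule and 5% reference rate also need a single definition.

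*Combined protocol and SAP*

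**What the plan says.** **Event.** Section 1.2.1 bases feasibility on "grade 3 or higher radiation pneumonitis or any grade 4 toxicity within 3 months after the completion of radiation treatment". The first-stage rule in 12.1 stops a cohort if 2 or more of the first 12 "patients were to experience grade 3 or higher radiation pneumonitis or any grade 4 toxicity within 3 months of finishing radiation". The final rule in 12.1 accepts a cohort with at most 2 events in 26; Section 6.3 gives the same composite but accepts at most 3.

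**Other wording of the window.** Section 12.1 also says "the feasibility of proton radiation will also be compromised by any grade 4 effect occurring within 3 months of treatment", which does not say whether the 3 months run from the start or the end of treatment. Sections 8.1.1 and 12.3 make patients evaluable for toxicity from first treatment.

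**Attribution and collection.** Section 5.3 states "Concomitant chemotherapy as dictated by protocol or the treating physician is allowed". Section 6 collects "All radiation related grade 2 and greater adverse events" from the start of radiation to the final visit. Section 9 defines and collects adverse events whatever their cause, up to 30 days after the last dose. Section 9.2.4 has a five-level attribution scale, but no statement of the primary event refers to it.

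**Reference rate.** Section 12.1 calls protons feasible "if the rate of grade 3 or higher radiation pneumonitis within 3 months of treatment were no more than 5" per cent, and then gives its operating characteristics for the wider composite. The supporting evidence in 2.2 is on pneumonitis: "The weighted average for grade 3 RP in these series using the RTOG scale is around 3.3" per cent.

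**Extra clause.** Section 12.1 adds "as well as skin toxicity and pericarditis" as compromising feasibility, with no grade and no count; 6.3 has a similar clause.

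**The concern.** A two-stage safety rule with limits this small depends on exactly which events count. One event separates continuing from stopping at 12 patients (1 against 2), and feasible from not feasible at 26 under 12.1 (2 against 3). The wording leaves four things open:

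- whether a death from a toxicity other than pneumonitis is a failure;
- whether an event during radiation counts;
- whether an event caused by concurrent chemotherapy counts;
- what skin toxicity or pericarditis below grade 4 does to the decision.

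The first is the most serious, because the literal rule passes over the gravest outcome. In addition, the rate offered as acceptable is argued for one component and applied to the whole composite, so a reader cannot tell what rate of other severe toxicity the sponsor is prepared to accept.

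**Working it through.** **1. Grade wording.** Sections 1.2.1, 6.3 and 12.1 all give pneumonitis an open upper end and give other toxicity as grade 4 alone. The authors spell out an upper range elsewhere: Section 2.2 speaks of grades 3-5 for pulmonary toxicity. The CTCAE table in the appendices has a separate grade 5 column, which is death for most conditions listed. No section counts a non-pneumonitis death as a failure.

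**2. The plan's own figures.** Inputs from 12.1: 12 patients, then 26 in total (14 more); stop if 2 or more of 12; feasible if 2 or fewer of 26.

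- P(stop at 12) = 1 − P(X1 = 0) − P(X1 = 1), with X1 ~ Bin(12, p).
- P(feasible) = P(X1 = 0)·P(Bin(14, p) ≤ 2) + P(X1 = 1)·P(Bin(14, p) ≤ 1).

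At p = 0.05:

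- P(stop) = 1 − 0.5404 − 0.3413 = 0.118 (stated 12%).
- P(feasible) = 0.5404 × 0.9699 + 0.3413 × 0.8470 = 0.813 (stated 81%).

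At p = 0.15:

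- P(feasible) = 0.1422 × 0.6479 + 0.3012 × 0.3567 = 0.200 (stated 20%).

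All three reproduce. With the limit of 3 in 6.3, P(feasible) is 86.9% at 5% and 31.7% at 15%, so only the limit of 2 gives the stated pair.

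**3. The pneumonitis evidence.** From the table and text in 2.2, grade 3 events are 5 + 12 + 2 + 2 + 0 = 21 (2% of 77 rounded to 2). Patients are 41 + 294 + 77 + 189 + 38 = 639. 21/639 = 3.29%, matching the stated 3.3%. No rate for other grade 4 or 5 toxicity is given.

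**4. What the 5% leaves for other events.** Let q be the rate of other grade 4-5 events that count. It is an assumption, taken as independent of pneumonitis. Composite = 1 − (1 − pneumonitis rate)(1 − q). Final limit 2 of 26.

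| q (assumed) | Composite, pneumonitis 5% | P(feasible) | Composite, pneumonitis 3.3% | P(feasible) |
|---|---|---|---|---|
| 0.5% | 5.5% | 78% | 3.8% | 89% |
| 1% | 6.0% | 75% | 4.3% | 86% |
| 1.7% | 6.6% | 70% | 4.9% | 82% |
| 2% | 6.9% | 68% | 5.2% | 80% |
| 5% | 9.8% | 47% | 8.1% | 59% |

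With pneumonitis at 3.3%, the composite reaches 5% when q = 1 − 0.95/0.967 = 1.76%. With pneumonitis already at 5%, nothing remains.

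**5. The opposite direction.** If the wording leaves events uncounted, unsafe cohorts pass more often. At a true composite of 15%, counting 90% of events (an assumed share) gives an effective rate of 13.5% and P(feasible) of 26.2%. Counting 80% gives 12% and 33.7%. The stated figure is 20%.

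**The case against.** Several stronger readings are tempting, and the documents do not support them.

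- **That chemotherapy events count against protons.** No section says so. Section 6 collects radiation-related events, and 5.2.3 gives hospitalisation for neutropenia on concurrent chemotherapy as an example of an event unrelated to protocol therapy. What stands is that the endpoint has no attribution rule and that Sections 6 and 9 differ on what is collected.
- **That events during radiation are excluded.** The objective and the first-stage rule point that way. The looser window wording in 6.3 and 12.1, evaluability from first treatment, and weekly toxicity assessment during radiation in the study calendar point the other way. The window is ambiguous; it is not a clear exclusion.
- **That the 81% is wrong or falls.** It is stated for the composite and is correct at a 5% composite rate. The lower acceptance figures come from an assumed rate of other events; for small rates and 3.3% pneumonitis, acceptance is at or above 81%. The protocol also expects less toxicity with protons. What stands is that the 5% is not justified for the composite.
- **That a death would go unnoticed.** Serious events during treatment and to 30 days afterwards go to the principal investigator within 24 hours regardless of attribution (9.5.1), and the safety committee reviews toxicity and may receive death summaries (10.2). The gap is in the count that decides stopping and feasibility.
- **That skin toxicity and pericarditis are certainly outside the rule.** The clause in 6.3 could be read as giving examples of grade 4 effects, which do count. The wording in 12.1 fits that reading less well, so it remains a drafting ambiguity.

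**Conclusion.** The point holds as a defect of definition. Applied literally, the counting rule omits a grade 5 toxicity other than pneumonitis, and at these limits one event can change a cohort's outcome. The window, attribution, and the status of skin toxicity and pericarditis are unresolved, which is less than saying they are set wrongly.

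The operating characteristics are sound for composite rates of 5% and 15% with a final limit of 2. The weakness is that the feasibility sentence and its evidence concern pneumonitis alone. How much this matters depends on a rate the documents do not give. Over an assumed 0.5-5% of other events, independent of pneumonitis, acceptance is 78-47% with pneumonitis at 5% and 89-59% with pneumonitis at 3.3%; in the second case it is at or above the stated 81% while other events are about 1.7% or less. These ranges are illustrations, not estimates. The grade 5 gap rests on the wording alone and needs no assumption.

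**What to change.** Use one definition, identical in 1.2.1, 6.3 and 12.1: *radiation pneumonitis of grade 3 or above, or any other toxicity of grade 4 or 5 that is at least possibly related to radiation (Section 9.2.4), from the first fraction to 3 months after the last.*

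In the same edit:

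- list unrelated grade 4-5 events beside the count, so that attribution decisions can be seen;
- reword the feasibility sentence so that 5% refers to the composite, and say why that rate is acceptable;
- reconcile the skin toxicity and pericarditis clause with the counting rule;
- align collection in Sections 6 and 9 with the endpoint, including the 3-month window;
- reconcile the final limits in 6.3 (at most 3 of 26) and 12.1 (at most 2), noting that only 2 reproduces the stated 81% and 20%.

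Cost: no extra patients or procedures, but more than a wording change. Attribution adds judgement. Enrolment began in August 2011 and the accrual target has already been adjusted on observed data (12 and 12.1.1), so redefining the event needs an IRB-approved amendment and re-review of patients already treated against the new definition.

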1.3 Secondary Objectives

1.3.1 The endpoints in these objectives are descriptive and will form the basis for designing future studies. The Common Terminology Criteria for Adverse Events (CTCAE) version 4 will be used for grading toxicities.

- To evaluate the rate and severity of acute skin toxicity
- To evaluate the rate and severity of radiation pneumonitis, a sub-acute toxicity
- To evaluate the rate and severity of late skin toxicity
- To evaluate cosmetic outcome and patient satisfaction with cosmetic outcome

CONFIDENTIAL

This document is confidential. Do not disclose or use except as authorized.

- To evaluate acute and late toxicity of breast reconstruction following proton radiation
- To evaluate the need for unplanned additional surgery for breast reconstruction
- To evaluate early signs of cardiac effects from radiation therapy using Strain Echocardiogram

1.3.2 To describe the 5 year progression free survival rate of patients with breast cancer treated with proton radiation.

2. BACKGROUND

2.1 Proton Radiation

Radiation therapy (RT) has been proven an essential component of therapy for breast cancer. Unfortunately, radiation also carries substantial risks to surrounding healthy tissues and organs. Well documented side effects of radiation to the breast and/or chest wall include pulmonary and cardiac toxicity due to unavoidable delivery of radiation therapy to the heart and lungs. Proton radiation is a form of particle radiation that can deliver radiation therapy to the chest wall and lymphatics with near complete avoidance of the heart and lung. Proton radiation therapy is currently available at only a handful of radiation treatment centers in the United States. The Massachusetts General Hospital has the longest experience in the US and has been using protons for clinical treatments since 1961. Seven other proton centers have since opened in the United States, five within the past 5 years. Mainly due to limited availability and increased costs, the clinical use of protons has been limited, for the most part, to tumors requiring high doses and/or in close proximity to critical structures (brain, spinal cord, etc) and for the treatment of pediatric malignancies.¹⁻⁵ Over the past several years, the realization of the substantial benefit of this radiation modality has been recognized. Despite substantial capital and operational costs, several proton facilities in both the private and academic sectors are in planning or construction phases. Furthermore, several companies are actively researching more efficient and less expensive machines capable of delivering proton radiation. Given the increased availability of this treatment, it is important to explore in academic centers the potential benefit for additional malignancies, such as breast cancer. While several centers have published comparative planning studies and hypothesize that protons will provide a decrease in acute and late toxicities for patients requiring radiation therapy for advanced breast cancer, no clinical studies have been performed or reported to date for this group of patients. The Paul Scherer Institute in Switzerland plans to open a protocol for delivery of radiation for patients with advanced breast cancer early next year (personal communication, [name].).

Protons are charged particles that enter tissue delivering a small and constant dose until near the end of the proton range where the majority of dose is delivered.⁶ Beyond this

CONFIDENTIAL

This document is confidential. Do not disclose or use except as authorized.

distal portion of the proton beam no dose is delivered. This enables complete sparing of uninvolved tissues and organs distal to the target volume. This is in contrast to photons that must deliver dose both proximal and distal to region targeted as demonstrated in Figure 1. Proton radiation is prescribed in Gray(RBE) as opposed to Gray, which is used for prescribing photon radiation. This takes into account the slightly higher Relative Biological Effectiveness (RBE) of protons. Thus, for a given prescribed dose the biological effect in tissues is the same for protons and photons and benefits are due to physical properties of the proton beam.^{7,8,9} The benefit of delivering radiation with protons versus photons is derived from the physical properties of the proton particle itself. Protons as are planned in this study will deliver the same dose to target structures. Advanced forms of photon radiation therapy do exist, but are suboptimal as the physical properties of photons necessitate delivery of dose beyond the target. Intensity modulated photon radiation therapy (IMRT) is the most advanced form of photon radiation currently available. IMRT accomplishes excellent conformity to target volumes while decreasing high dose to specified avoidance structures. This is accomplished by a sophisticated computer planning system and delivery of radiation through multiple small fields and beam angles.¹⁰ One of the major disadvantages of IMRT is the increase in low dose to a larger amount of normal tissue. This greater volume of tissue receiving radiation is of particular concern for young patients with a high likelihood of surviving their malignancy and a higher risk of developing a radiation induced malignancy. Low doses to a large volume of pulmonary tissue is also a concern.¹¹⁻¹²

At this time, the predominant mode of proton delivery is through passive beam scattering methods or “3D conformal” proton therapy. Scattering foils, range compensators, and apertures are designed to deliver a homogeneous dose distribution to the target with optimal dose conformity at the distal target region for each field.⁶ There is some degree of intensity modulation in these proton plans, but increased modulation is possible through pencil beam scanning techniques which became available only recently. Plans that use scanning techniques are referred to as Intensity Modulated Proton Therapy (IMPT) plans.¹³⁻¹⁴ Similar to Intensity Modulated Radiation Therapy (IMRT), IMPT refers to plans that deliver a homogenous dose to the target with the superimposition of individually inhomogeneous fields.⁵ Although this increases the complexity of the plan, it allows for increased dose-shaping capabilities with optimal conformity not only at the distal region of the target but also to the proximal target edge. IMPT may also facilitate the treatment of large areas without matching of fields (which introduces “cold” and “hot” areas at the match line of a plan) and allows for a decrease in the dose to skin if this is desired. For PMRT, the skin and subcutaneous tissue is the target and the goal is to deliver full dose or near full dose. “Bolus” or electron radiation is often used to increase dose to the skin. For this protocol, treatment plans will be established to deliver a dose to the skin comparable to these treatment techniques. Therefore, we do not anticipate greater skin toxicity compared to standard treatment plans, but patients will be monitored closely for this toxicity.

CONFIDENTIAL

This document is confidential. Do not disclose or use except as authorized.

Despite advances in photon techniques, homogeneous coverage of targets and optimal sparing of cardiac and pulmonary structures can be a challenge, especially for the treatment of locally advanced breast cancer in the setting of breast reconstruction. Clinical data with protons is not available for treatment of whole breast, chest wall, or regional lymphatic irradiation, but studies evaluating the dosimetry for such cases studies have been reported.^{5, 15} Lomax et al, reported results of comparative treatment planning using standard photons, IMRT, and spot scanning proton therapy (IMPT) for radiation of the breast and regional nodes for a patient with left sided breast cancer.⁵ The IMPT plan provided improved target coverage and dose homogeneity, decreased dose to cardiac and pulmonary structures, and provided the lowest integral dose to surrounding tissues. Johansson et al also examined the potential benefit of protons for left sided locally advanced breast cancer.¹⁵ This study evaluated two conventional plans (tangents, and mixed photon/electron technique), IMRT, and 3D conformal proton treatment plans for eleven patients. The authors used normal tissue complication probabilities (NTCP) for evaluation of plans.¹⁶ Mean calculated NTCP values for cardiac mortality and pneumonitis were substantially lower for the proton plan compared to all other plans. Although IMRT reduced the NTCP for the heart, it did not decrease NTCP for radiation pneumonitis in this study. Both conventional and IMRT plans showed increased integral dose as compared to the proton plan. In summary, the authors concluded that proton therapy has the potential to offer a major advantage in decreasing the risk of normal tissue complications in the treatment of left sided node positive breast cancer. At MGH, we have also analyzed plans for both 3D conformal protons and IMPT for the treatment of patients requiring post-mastectomy radiation therapy (PMRT) for left sided breast cancer. Proton plans were compared to treatment plans using partially wide tangent fields (PWTF) and a mixed photon electron (E/P) technique for eight patients. 3D proton plans were superior to PWTF and E/P technique. (Figure 2 & 3). Given the increased number of proton facilities and heightened public awareness of this modality, it is of utmost importance that a clinical trial be performed to evaluate toxicity and clinical outcomes for patients treated with proton radiation (3D-CRT or IMPT) for patients requiring left PMRT. In summary, all studies indicate a decrease in the amount of heart and lung in the treatment field that receives ANY dose of radiation (high dose or low dose). Decades of experience as well as physics research and clinical outcomes indicate that these dose distributions are accurate. Therefore, clinically, this should result in a decrease in toxicity for patients treated with protons. The ultimate question is whether or not the increased cost of protons warrants the decreased risk of side effects. As the number of proton facilities increase, it is likely that the cost of treatment will decrease and that additional centers will explore and administer protons for locally advanced breast cancer. The intent of this study is to establish treatment plans for patients with technically challenging anatomy for adequate treatment planning with modalities that are currently more widely available (photons and electrons). We propose to deliver protons on a clinical trial to patients with implants requiring IMN radiation or for patients with unfavorable cardiac anatomy (as defined by $\geq 5\%$ of the heart receives ≥ 20 Gy and/or LAD receives ≥ 20 Gy with conventional planning) as the patients are the most challenging to adequately treat with standard photon and/or electron radiation therapy. These patients often require removal or manipulation of implant to allow for delivery of

CONFIDENTIAL

This document is confidential. Do not disclose or use except as authorized.

radiation therapy to the chest wall and regional lymphatics without prohibitive amounts of heart and lung in the treatment field. In addition, we include patients with unfavorable cardiac anatomy. These patients also present a challenge for current treatment techniques.

